2. GLOSSARY OF ABBREVIATIONS & TERMS

Insert or delete information as required

Abbreviation	Description (using lay language)
MS	Multiple Sclerosis
RCT	Randomised Controlled Trial
MSOC	Multiple Sclerosis Online Course
MSOC - Feasibility	Multiple Sclerosis Online Course - Feasibility study
MSOC - RCT	Multiple Sclerosis Online Course – Randomised Control Trial
QoL	Quality of life
HRQOL	Health Related Quality of life
UoM	The University of Melbourne
HREC	Human Research Ethics Committee
NHMRC	National Health and Medical Research Council
DHQ	Dietary Habits Questionnaire
HADS	Hospital Anxiety and Depression Scale
MSQOL-54	Multiple Sclerosis Quality of Life-54 instrument
IPAQ-SF	International Physical Activity Questionnaire - Short Form
FSS	Fatigue Severity Scale
MAQ	Mindfulness Adherence Questionnaire
PDDS	Patient-Determined Disease Steps
PHC	Physical Health Composite
MHC	Mental Health Composite
MSPSS	Multidimensional Scale of Perceived Social Support
UWSE	University of Washington Self-Efficacy

4. INTRODUCTION/BACKGROUND INFORMATION

4.1 LAY SUMMARY

The Multiple Sclerosis Online Course (MSOC), both the intervention and standard-care arms, was delivered as part of a feasibility study (MSOC - Feasibility study) in April to June 2021. In the MSOC – Feasibility study 31 participants from Australia, New Zealand, and the United States completed the MS Online course (n=15 intervention course and n=16 standard-care course). Examination of the acceptability and usability in the MSOC – Feasibility study was conducted via quantitative and qualitative analyses, with the results of these analyses currently in preparation for publication in a peer-reviewed journal.

In the proposed study, we plan to perform a randomised controlled trial (RCT) utilising the results from the MSOC – Feasibility study. That is, the MS Online course has been modified and redeveloped to test the effectiveness of the MS Online intervention and standard-care courses in a large international RCT (MSOC – RCT).

This RCT will analyse participant uptake and retention, adoption and adherence to lifestyle recommendations and health outcomes at baseline, and 6 months, 12 months, and 2.5 years after completing either the MS intervention or standard-care course. The significance of this study is that the RCT will test:

- 1) whether an MS Online educational intervention course, compared with a standard-care course, can change behaviour in people with MS and
- 2) whether an MS online educational intervention course, compared with standard-care course, leads to superior improved health outcomes in people with MS.

4.2 INTRODUCTION

Although genetic factors are responsible for roughly 25% of the risk of multiple sclerosis (MS) onset, they play less of a part in disease progression. By contrast, disease progression and disability are associated or influenced by environmental factors including modifiable lifestyle behaviours. These risk factors include smoking, a diet high in saturated fat and low in omega-3 polyunsaturated fatty acids, lack of physical activity, inadequate vitamin D level, and stress. The amelioration of these risks is associated with a reduction in the chronic inflammatory state associated with MS (Fragoso, 2014), and subsequent improved health outcomes including improved mental and physical health quality of life (Hadgkiss, Jelinek, Weiland, et al., 2015; Jelinek et al., 2013; Marck et al., 2014), reduced relapse rate (D'Hooghe M, Nagels, Bissay, & De Keyser, 2010), depression risk (K. L. Taylor et al., 2014), clinically significant fatigue (T.J. Weiland et al., 2015; T. J. Weiland et al., 2015), and less disability and symptom burden (Fitzgerald et al., 2018; Jelinek et al., 2016). Lifestyle modification of these risk factors represents an effective, low cost and low risk intervention in MS.

Studies of a lifestyle modification programs for MS including evidence-based recommendations regarding diet, exercise, stress management, sun exposure, and vitamin D delivered via intensive face-to-face residential workshops. These workshops have demonstrated 11.3% and 19.5% improvement in overall quality of life at one and 5-year time-points post workshop, respectively, compared to baseline measures (Hadgkiss et al., 2013), and that behaviour change was feasible and sustainable (Marck et al., 2018). However face-to-face interventions are resource intensive and present potential barriers to participation for people with MS, including geographical, financial and disease specific factors such as fatigue and mobility. The COVID-19 pandemic has highlighted the highly unpredictable ability to travel and presented further MS specific challenges relating to potential immunosuppression and subsequent vulnerability of participants in face-to-face education.

Web-based interventions have shown great efficacy at promoting positive lifestyle changes in a range of populations for a variety of medical conditions (Bardus, Smith, Samaha, & Abraham, 2016; Bossen, Veenhof, Dekker, & de Bakker, 2014; Knittle et al., 2018; Kohl, Crutzen, & de Vries, 2013; Neve, Morgan, Jones, & Collins, 2010; Olson, 2016), including MS (Fischer et al., 2015; Hind et al., 2014; Kirsten van, Trecia, & Rona, 2015; Moss-Morris et al., 2012). However, there is a paucity of studies that incorporate multiple lifestyle recommendations into one program. To date, no evidence-based lifestyle modification program for people with MS has been translated into a web-based Online intervention that has been tested in a randomised controlled trial (RCT) with long-term follow-up.

People with MS are a highly motivated population that show modest levels of engagement and retention in lifestyle management programs, and previous Online self-assessments have found favourable levels of engagement and retention in the short- and long-term (Jongen et al., 2017). An Online educational intervention for people with MS would potentially alleviate resource issues, ameliorate barriers of geography and mobility and meet all the requirements post pandemic of reaching an already potentially vulnerable population.

Our research team, together with a community advisory group of people with MS, has developed the Multiple Sclerosis Online Course (MSOC) in two arms: the MS online intervention course and the MS online standard-care course. Each course delivers educational modules regarding the biological basis of MS and preventing MS in family members through lifestyle modification in diet, exercise, stress reducing activities, sunlight and vitamin D, omega 3 and smoking and alcohol intake. The intervention course provides evidence-based recommendations for lifestyle modification across these modules, delivered via a mixture of videos, presentations, and reading components. The

standard-care course is similar in structure and functionality but contains standard MS health recommendations from a range of international MS websites. Results from the MSOC – Feasibility study (The University of Melbourne HREC 1851781.1) comprising the MS Online intervention course versus the MS Online standard-care course demonstrated that people with MS completed both the intervention and standard-care course at satisfactory rates, believed the course was readily accessible and enjoyable, and participated in follow-up evaluation (quantitative and qualitative manuscripts currently in preparation).

Our research question is: Will a Multiple Sclerosis Online Course that delivers evidence-based lifestyle modification recommendations to people with MS (the intervention) result in greater post-intervention sustained lifestyle behaviour change and improved health outcomes compared with a standard-care course (the control)?

Results of the RCT will be disseminated through international conference presentations and in peer-review international journals with open access to ensure research findings are readily available for people with MS, clinicians and the general public.

Following completion of the RCT, the MS Online Course will be made available free of charge to people with MS worldwide via the Overcoming MS Charity to empower people with MS to adopt a program of positive lifestyle change to improve their health and well-being.

Potential benefits of participants enrolling in the RCT:

Increasing evidence in the scientific literature suggests that lifestyle modification could be a point of intervention for improving quality of life and clinical outcomes in people with MS. In the NEU at the University of Melbourne we have developed an online course that will deliver the relevant information to people with MS that has the potential to improve their health outcomes. While we have developed an intervention course and a standard-care course, both online courses have the potential to improve health outcomes in people with MS. Topics included in the online courses that have been associated with improved health outcomes which may prove to be beneficial to RCT participants are outlined below. However, findings in the literature are conflicted and emphasises there is need for a RCT to directly identify any causal associations between lifestyle factors and health outcomes (our proposed MSOC – RCT study):

Diet

Topics covered in the MS-online related course include a module on diet quality. Several studies have found better quality-of-the-diet is associated with reduced relapses, (Simpson-Yap et al., 2020) and disability. (Fitzgerald et al., 2018; Jelinek et al., 2016; Simpson-Yap, Nag, Probst, Jelinek, & Neate, 2021) Other studies have found diet is associated with improved QoL. (Evers, Heerings, de Roos, Jongen, & Visser, 2021; Hadgkiss, Jelinek, Weiland, et al., 2015; Marck, Probst, Chen, Taylor, & van der Mei, 2021) In particular, a study from our group of a large international cohort found a 10% improvement in diet quality as assessed by the Diet Habits Questionnaire was associated with 6% and 5% higher physical and mental-QoL at baseline, respectively, and this was most evident for fruit/vegetable and fat. (Hadgkiss, Jelinek, Weiland, et al., 2015)

Vitamin D

In a cross-sectional study, Vitamin D supplementation was found to be associated with improved health outcomes in people with MS.(Jelinek et al., 2015) A further study by Simpson-Yap et al. found vitamin D supplementation was associated with higher physical and mental QoL in a cross-sectional analysis but only associated with higher physical QoL in a prospective analysis.(Simpson-Yap, Jelinek, et al., 2021) Other observational studies have found lower vitamin D levels are associated with increased risk of MS and progression.(Duan et al., 2014; Martinez-Lapiscina, Mahatanan, Lee, Charoenpong, & Hong, 2020)

Omega-3

Studies have found increased Omega-3 intake or oily fish consumption is associated with improved health outcomes in people with MS. In particular, Jelinek et al. found Omega-3 intake improved QoL and reduced relapses,(Jelinek et al., 2013) and Coe et al. found consuming fish decreased fatigue.(Coe et al., 2021)

Stress relief

Observational studies have found stress reduction can reduce exacerbations in people with MS and improve QoL and emotional wellbeing in people with MS.(Mohr et al., 2012; Senders et al., 2019; P. Taylor, Dorstyn, & Prior, 2020) In particular, the randomised controlled trial by Mohr et al. demonstrated stress management training reduced disease activity by reducing the presence of new lesions in the brain of people with relapsing-remitting MS.(Mohr et al., 2012) However, other studies found stress reduction did not improve QoL.(Agland et al., 2018)

Physical activity

Observational studies have found physical activity is associated with increased energy and social functioning and improved physical and mental health outcomes.(Marck et al., 2014; Marck, Learmonth, Chen, & van der Mei, 2020; Motl & Gosney, 2008)

Key questions:

Does participation of people with MS in the MS Online intervention course change lifestyle behaviours compared with participants in an MS Online standard care course in the:

- 1) Short-term
- 2) Medium-term

What is the effect on participant health outcomes from different levels of adoption and adherence to lifestyle recommendations in the MS Online intervention course compared with MS Online standard-care course with respect to:

- 1) Quality of life

- 2) Fatigue
- 3) Depression
- 4) Anxiety
- 5) Disability
- 6) Self-efficacy

4.3 BACKGROUND INFORMATION

Lifestyle factors are known to affect the progression of multiple sclerosis (MS). Studies of participants with MS attending an evidence-based lifestyle modification program, delivered via face-to-face workshops in Australia, have demonstrated improved mental and physical health, reduced relapse rate and improved quality of life over three years follow-up, and that behaviour change has been found to be feasible and sustainable. However, the face-to-face modality of this educational intervention is resource-intensive and accessibility may be impeded by geography, cost, and MS-specific factors such as illness, fatigue, and disability. Furthermore, the COVID-19 pandemic has highlighted the unpredictable ability to travel and the importance of flexibility of health-related education.

The Neuroepidemiology Unit, Melbourne School of Population and Global Health, has developed the Multiple Sclerosis Online Course (MSOC) to deliver a widely accessible and user-friendly educational tool for people with MS. The course aims to deliver the best available evidence regarding lifestyle-related risk factors in the development and progression of MS and behaviour modification to improve health outcomes.

Two forms of the course were developed:

1. an MS Online intervention course based delivering evidence-based information regarding modifiable lifestyle related risk factors implicated in disease progression; and
2. an MS Online standard-care course, similar in format and presentation, but containing general information sourced from standard MS websites. Both courses have seven modules delivered over six weeks.

A feasibility study involving the delivery of the intervention and standard-care course was conducted from April to June 2021 (MSOC – Feasibility). This study assessed the primary outcomes of attrition in both the intervention and standard-care arm. Secondary outcomes assessed the completion of the baselines survey, and quantitatively assessed learnability, accessibility, and desirability via a Likert scale follow-up survey. A qualitative analysis examining motivation, expectations and outcomes was also conducted. Based on the MSOC – Feasibility study, we have modified recruitment, functionality, and the community forum aspects of the course. We now aim to test the effectiveness of the intervention arm of the course compared with the standard-care arm in a larger randomised controlled trial (MSOC - RCT).

Choice of comparators in RCT:

The proposed study aims to prospectively determine whether an Online MS Lifestyle Modification Course (the intervention arm) can deliver an evidence-based educational intervention that results in behaviour change which is sustained and is translated into improved health outcomes for people

with MS, and whether these effects are superior to the Online standard-care course (the control arm).

In this RCT, we will be comparing two interventions/products that were developed by researchers at the Neuroepidemiology Unit (NEU) at the University of Melbourne:

1. the MS Online intervention course that delivers information on diet, exercise, Vitamin D and omega-3 supplementation and stress relief/meditation
2. the MS Online standard-care course that delivers standard MS-related information that can be obtained through publicly-available Websites.

In people with MS, we aim to compare health outcomes of people enrolled in the intervention (the MS Online intervention course) with the control arm (the MS Online standard-care course) by assessing:

- assess the uptake and maintenance of recommended lifestyle modifications in a cohort of people with MS after undertaking an MS online educational lifestyle course compared with people undertaking an online standard-care course.
- assess whether people with MS undertaking an MS online educational lifestyle intervention course results in improved clinical outcomes and health outcomes of depression, fatigue, disability, and quality of life over the short-term and medium-term compared with people undertaking an online standard-care course.

5. STUDY OBJECTIVES

5.1 HYPOTHESIS

People with MS who undertake the MS Online intervention course (the intervention arm) delivering evidence-based lifestyle modification education will have sustained behaviour change and improved health outcomes that are superior to the health outcomes in people with MS undertaking the MS Online standard-care course (the control arm).

5.2 STUDY AIMS

To quantitatively and qualitatively assess the arms of the Multiple Sclerosis Online Course in an RCT (the MS Online intervention course and MS Online standard-care course). We aim to measure:

- 1) The degree of engagement with and participation in the course
- 2) Adoption of lifestyle behaviours change following course completion
- 3) Adherence to lifestyle behaviour change over time
- 4) Short-term and medium-term health outcomes and
- 5) To compare all these outcomes between both arms.

Overall, the proposed RCT will enable a causal relationship between lifestyle factors and clinical and health outcomes to be examined.

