Primary Objectives:	
To determine whether participants adhering to lifestyle modification recommendations outlined in the MS Online intervention course have clinically significant increased health-related quality of life (HRQOL) in both domains of physical and mental health compared with participants following recommendations of the MS Online standard-care course. These outcomes will be examined in the short-term (6 and 12 months) and in the medium-term (2.5 years).
 
That is, we aim to determine whether participants in the Online intervention course following recommended lifestyle modifications have clinically significant and material increases in Physical Health Composite (PHC) and Mental Health Composite (MHC) scores, as derived from the validated tool designed to measure HRQOL in people with MS (MSQOL-54) compared with participants following recommendations of the Online standard-care course.

Secondary Objectives	
To determine whether participants following the lifestyle modification recommendations in the Online MS intervention course have improved depression, anxiety, fatigue, disability and self-efficacy in the short-term and medium-term compared with people following recommendations of the Online MS standard-care course.

Inclusion Criteria:	
Eligible participants must:
 
 1. Be able to read, write, and speak English; 2. Be 18 years old or over; 3. Have a confirmed diagnosis of relapsing-remitting MS by a neurologist preceding recruitment; 4. Be able to access the internet and be able to view sessions.
Exclusion Criteria:	
Exclusion criteria of participants include:
 
 1. Experiencing any serious co-morbid chronic illness or neurological illness/injury other than MS that would threaten regular participation or significantly affect the outcome measures in its own right, such as motor neurone disease or stroke, as determined by the study investigators; 2. Currently participating in another study or self-management program involving modification of lifestyle.
Number of Planned Participants:	
1054 participants, 527 in each arm at 1:1 allocation (intervention and standard-care arm)

Investigational product:	
Not applicable

Safety considerations:	
Participation in the study poses no physical risk to participants as the proposed RCT involves taking part in an Online MS

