5.3 OUTCOME MEASURES

QUANTATIVE OUTCOMES

Lifestyle behaviour of participants will be assessed at baseline and 6 months, 12 months and 2.5 years after completion of the Online MS course (intervention or standard-care). Lifestyle/behaviour outcomes to be measured include:

a. Exercise

To assess physical activity we will use The International Physical Activity Questionnaire - Short Form (IPAQ-SF), a 7-item 7-day recall of frequency and duration of vigorous and moderate physical activity, walking, and sitting assessed in nine items (Craig et al., 2003). The IPAQ and its short form have been validated in several studies and populations globally, and the long form has been used previously for people with MS (Stroud, Minahan, & Sabapathy, 2009; Weikert et al., 2012).

b. Diet

Since we aim to assess diet broadly with a particular consideration for fats, we will modify the Diet Habits Questionnaire (DHQ) (McKellar et al., 2008). The original 24-item DHQ has eight dietary sub-scores, and assesses saturated and unsaturated fat intake, fruit and vegetable, fibre, takeaway, snack habits, and omega-3 consumption, among other estimates. In our modified version, we removed three items regarding sodium intake, and one item on alcohol was replaced with an alternate alcohol assessment measure. We added a researcher-devised item regarding oily fish consumption that was separate from the DHQ: "How often do you eat oily fish such as sardines, mackerel, herring, salmon, tuna or trout? (Never; Less than once a week; About 1 - 2 times a week; About 3 - 4 times a week; At least 5 times a week) and options regarding "I don't eat meat" and "I don't eat dairy".

c. Alcohol consumption

Volume and frequency of alcohol consumed will be queried. In Australia a standard drink is considered to be 10 grams of ethanol. Frequency of binge drinking, defined by the Australian Bureau of Statistics as more than 7 drinks a week for men, and more than 5 for women, will be queried.

d. Smoking

Smoking status (never/ex-smoker/current smoker) will be queried. For current smokers, typical number of cigarettes per week will be queried along with the total years they have been smoking. For ex-smokers, their typical number of cigarettes per week when they smoked will be queried, as well as the total years they smoked and the duration since they quit smoking.

e. Omega-3 uptake

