- V. Interested participants meeting the study eligibility criteria (Refer to Section 6.2 and 6.3 for eligibility criteria) after completing the eligibility questions will be emailed a participant information form and consent form. Once participants have provided their consent by ticking a box online, participants will be emailed a link to the baseline questionnaire to obtain demographic data and obtain data on lifestyle and outcome measures (Section 4.3, Table 1). Interested participants not meeting the study eligibility criteria will be excluded and notified by email that they were not eligible to participate in the study and thanking them for their interest.
- VI. Participants will be randomised to either the MS Online intervention course or the MS Online standard-care course at a ratio of 1:1 using simple randomisation. Randomisation will occur over a 2-week period after recruitment of eligible participants.
- VII. Participants will undertake the MS Online course (intervention arm or standard-care arm) over a 6-week period. Note, each arm is of comparable length and content-type (video, interviews, images, interactivity), to minimise variability in 'dose' received between intervention and standard-care groups. Both courses will follow a similar structure throughout, limiting differences in how the content of the course is presented.
- VIII. Patient-reported outcomes measures (Section 4.3, Table 1) will be determined after a period of 6 months, 12 months and 2.5 years after the completion of the MS Online course. This will involve participants from the MS Online intervention arm and the MS Online standard-care arm completing validated questionnaires online (following instructions and reminders, if necessary, from study team members). These measures will determine participants adherence to lifestyle recommendations of the Online intervention and standard course with respect to diet, exercise, omega 3 intake, vitamin D intake, meditation and sun exposure (Table 1). Health outcomes related to participant's quality of life, depression, anxiety, fatigue, disability and self-efficacy.
- IX. The primary objective of the study will be assessed at the 12-month and 2.5 year follow-up. That is, Health-related quality of life (HRQOL) calculations for Physical Health Composite

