The complete patient-reported questionnaire with approximately 150 questions has been found to take approximately 60 minutes to complete. Participants will be able to login and complete this questionnaire over time. The participants will be requested to complete this questionnaire on four separate occasions (baseline, 6 months, 12 months and 2.5 years) and due to previous studies that we have performed within the Neuroepidemiology Unit utilising questionnaires of a similar length over 7.5 years ((Marck et al., 2018; Weiland et al., 2018), we do not believe the questionnaire will create an unacceptable burden on participants.

Quantitative data analysis:

We will measure adherence to lifestyle modification recommendations in people with MS enrolled in the MS Online intervention and the MS Online standard-care arm (control) using validated patient-reported questionnaires.

We will examine and compare clinical and health outcomes of depression, anxiety, fatigue, disability, self-efficacy and quality of life in people with MS in the short-term (6 months and 12 months) and medium-term (2.5 years) in people enrolled in the MS Online Intervention course arm and people enrolled in the MS Online standard-care course arm.

Statistical analyses will enable us to examine whether a causal relationship exists between lifestyle factors and clinical and health outcomes in people with MS. These analyses are anticipated to be completed within 6-12 months of collecting data for short-term and long-term analyses, respectively.

Qualitative data:

Qualitative data will comprise edited transcripts of recordings from semi-structured interviews from 15 randomly selected participants from the intervention arm and the standard-care arm carried out within one month of completing the MS Online course and 12 months after completing the MS Online course (the same people will be interviewed at both time points).

Interviews will be digitally recorded and transcribed by voice recognition software. Data will be stored in a re-identifiable format and encrypted files will be securely stored as described in Section 10.

Qualitative data collection feasibility:

The qualitative component of the MSOC – RCT is similar to the qualitative component of the MSOC – Feasibility study we performed. This interviewing technique was found to be both effective and participants reported positive feedback following interviews.

Qualitative data analysis:

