8. PARTICIPANT SAFETY AND WITHDRAWAL

8.1 RISK MANAGEMENT AND SAFETY

There will be no physical distress to participants in the proposed study as the study involves watching an educational course and completing questionnaires online. The exercise component of the MS Online Course in both arms of the study recommends a gentle exercise regimen, if participants decide to implement recommendations, that would not be expected to cause harm.

The research team in conjunction with participants involved in the qualitative interviewing component of the MSOC – Feasibility study found that the MS Online course, questionnaires and qualitative interviewing posed very low psychological distress to participants.

While we do not anticipate potential psychological distress, the following contingency plans will be implemented to address any psychological distress that may arise:

Quantitative research risk management

To address any psychological distress associated with completing online questionnaires at baseline and after 6 and 12 months and 2.5 years after completing the MS Online Course, links will be

provided at the end of questionnaires to country-specific help resources that the participant could access in the event that completing the questionnaires has raised issues for the participant. Participants will also be provided with the contact details of study team members and reminded that they can make contact with a team member if completing the questionnaires has raised any issues for them.

With regards to the HADS survey, while it is a validated tool for assessment of depression, it is not a diagnostic tool. However, we will also provide relevant country-specific resources and/or provide information/links to country-specific help/information at the end of the HADS. Notably, the HADS is the final questionnaire in the survey so this information will be provided directly after answering questions with the greatest potential to cause distress.

Qualitative research risk management

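### The causal aim is stated for lifestyle factors, but only the course is randomised, so the planned lifestyle and adherence regressions would give observational associations

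*Combined protocol and SAP*

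**What the plan says.** Three places name lifestyle factors as the cause to be studied:

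- Section 5.2 closes the aims by saying that "the proposed RCT will enable a causal relationship between lifestyle factors and clinical and health outcomes to be examined".
- Section 6.1, under quantitative data analysis, adds: "Statistical analyses will enable us to examine whether a causal relationship exists between lifestyle factors and clinical and health outcomes in people with MS".
- Section 4.2, after noting that the literature conflicts, speaks of the "need for a RCT to directly identify any causal associations between lifestyle factors and health outcomes" and names this trial as that RCT.

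Two further places frame questions by adherence. A key question in section 4.2 begins "What is the effect on participant health outcomes from different levels of adoption and adherence to lifestyle recommendations". The primary objective in the synopsis begins "To determine whether participants adhering to lifestyle modification recommendations outlined in the MS Online intervention course have clinically significant increased health-related quality of life".

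On design, section 6.1 states: "Participants will be randomised to either the MS Online intervention course or the MS Online standard-care course at a ratio of 1:1". Section 6.3 confirms simple 1:1 allocation to the two arms. Section 5.3 states: "Lifestyle behaviour of participants will be assessed at baseline and 6 months, 12 months and 2.5 years after completion of the Online MS course". Section 8.1, on the exercise component, describes the regimen as applying "if participants decide to implement recommendations".

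On analysis, section 9.3 (and the synopsis) names linear and log-binomial regression, with the quality-of-life models described as cross-sectional and prospective. Confounder assessment and adjustment are promised in general terms. No mediation, instrumental-variable or complier-effect method is named.

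**The concern.** A randomised trial supports causal statements about what was randomised. Here that is the offer of one course rather than the other. Behaviour after the course is a choice. People who are more motivated, less disabled or improving for other reasons may both adopt more of the advice and report better quality of life. Better health may also make exercise and meal preparation easier, which is reverse causation. An association between adoption and outcome can therefore appear whether or not the behaviours do anything.

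Section 4.2 uses the conflict in existing, largely observational, evidence to justify a trial. A regression of outcome on self-chosen behaviour inside the trial is the same kind of evidence. If the aims attach the trial's causal authority to it, a null comparison between courses could sit beside a lifestyle association that readers take as established cause. Section 4.2 says that results are meant for people with MS, clinicians and the general public.

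**Working it through.** **1. Stated causal target against what is randomised**

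| Question | Exposure | How the exposure arises | What protects the comparison |
|---|---|---|---|
| Course effect on behaviour and outcomes (aim 5 in 5.2; 4.3; 5.1) | Assigned course | 1:1 randomisation (6.1, 6.3) | Randomisation, if analysed as randomised |
| Lifestyle effect on outcomes (4.2, 5.2, 6.1) | Diet, exercise, omega-3, vitamin D, sun, meditation | Participant's choice, self-reported (5.3) | Confounder adjustment only |
| Effect of adherence level, or outcomes in adherers (4.2; synopsis) | Adherence | Participant's choice after randomisation | Confounder adjustment only |

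The causal wording belongs to the second row. Only the first row is randomised.

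**2. Could randomisation still identify a lifestyle effect?** Assignment could serve as an instrument, or a mediation analysis could be built on it. Both need stated assumptions, and none is given. There is one binary assignment and several behaviours promoted together, so it cannot separate their effects. The course might also act by other routes, for example its community forum, which would breach the assumption that an instrument works only through the behaviour studied.

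**3. How little confounding is needed (illustration).** The documents give no correlation between adoption and outcome, so 0.10 and 0.15 are assumptions.

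Number analysed: 1054 × (1 − 0.42) = 611.3, so about 611. Section 9.1 gives both 1054 and 42%, but can also be read as 1054 people with follow-up data, so both are shown.

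Test of a correlation r: z = atanh(r) × √(n − 3), two-sided p.

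| n | r = 0.10, atanh = 0.1003 | r = 0.15, atanh = 0.1511 |
|---|---|---|
| 611, √608 = 24.66 | z = 2.47, p ≈ 0.013 | z = 3.73, p ≈ 0.0002 |
| 1054, √1051 = 32.42 | z = 3.25, p ≈ 0.001 | z = 4.90, p ≈ 0.000001 |

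These correlations correspond to 1% (0.10²) and 2.25% (0.15²) of outcome variance.

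**4. Possible size in points (illustration).** A simulation of 2000 trials used n = 612 (306 per arm, from 527 × 0.58 = 305.7), an assumed SD of 20 and no effect of course or lifestyle on outcome. The course raised the lifestyle score by 0.5 of its within-arm SD. An unmeasured factor induced a within-arm lifestyle–outcome correlation ρ. Adherers were taken as intervention participants scoring above their arm's expected mean. Each test used a nominal two-sided 5% level.

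| ρ | Arms as randomised: false positives | Unadjusted lifestyle slope, points per within-arm SD (false positives) | Intervention adherers minus all controls, points (false positives) |
|---|---|---|---|
| 0 | 5% | 0.0 (6%) | 0.0 (5%) |
| 0.1 | 6% | 1.9 (67%) | 1.6 (11%) |
| 0.2 | 5% | 3.8 (100%) | 3.2 (37%) |
| 0.3 | 5% | 5.7 (100%) | 4.8 (66%) |

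The mean difference between arms as randomised was −0.02 points throughout. The biases agree with direct formulae. The slope is 20ρ / (1 + 0.25²), where 0.25² = 0.0625 is the variance that the 0.5 course shift adds to the lifestyle score: 1.88, 3.76 and 5.65. The adherer difference is 20ρ × 0.798, where 0.798 is the mean of the upper half of a standard normal: 1.60, 3.19 and 4.79. At ρ = 0.3 the adherer bias is close to the 5-point difference in section 9.1.

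**The case against.** A reader might infer that the plan presents observational results as proven cause. The documents do not go that far. Sections 5.2 and 6.1 say that a causal relationship will be examined, nothing has been reported, and section 9.3 uses the language of association. The causal sentence in 5.2 follows the aim of comparing the arms, and the one in 6.1 follows a paragraph on comparing outcomes by arm. Both could be loose shorthand for the effect of a lifestyle course. That reading stands as a possibility. It is weakened by section 4.2, where the RCT is to identify lifestyle causes directly and the effect of adherence level is a key question.

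A reader might also infer that confounding is ignored. It is not. Section 9.3 promises adjustment, the synopsis mentions clinical and demographic confounders, and Table 1 shows baseline outcomes, lifestyle, comorbidities, education, medication and social support being collected. The unadjusted slopes above are therefore not the planned analysis. What remains is that no confounder is named and that adjustment for measured variables need not remove motivation or reverse causation.

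A third tempting reading is that the lifestyle models can never support a causal statement. That is too absolute, because mediation or instrumental-variable methods can use the randomisation under stated assumptions. None is planned. Section 12 mentions a statistical analysis plan still to be developed, which might address this, but it is not in the documents as a separate text.

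Finally, the correlations are assumed, and small correlations reach significance at this size in any study. They show susceptibility and are not evidence of bias in this trial.

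**Conclusion.** The concern holds as a mismatch between a stated aim and the design. The comparison of courses supports a causal conclusion about assignment to the course, including its effect on behaviour and on outcomes. The lifestyle and adherence-level analyses, as specified, support associations only.

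This conclusion rests on the text alone and depends on no figure. The size is unknown. The range of p≈0.013 to p≈0.0002 at about 611 analysed assumes correlations of 0.10 and 0.15, 1054 randomised and 42% loss. The results in points also assume an SD of 20 and a particular form of confounding. The change is worth making before analysis because it alters what the trial may conclude.

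**What to change.** 1. In sections 4.2, 5.2 and 6.1, limit the causal claim to the effect of assignment to the intervention course versus the standard-care course, analysed as randomised.
2. Label the lifestyle–outcome and adherence-level analyses as exploratory and observational. This covers the key question in section 4.2 and the adherer wording of the primary objective in the synopsis, so that the causal primary comparison is the one between randomised arms.
3. In section 9.3, specify adjustment of these models for baseline outcome and baseline lifestyle, both already collected, and name the other confounders.
4. Make no causal claim from these models unless a mediation or instrumental-variable analysis is pre-specified with its assumptions. State that a single binary assignment cannot separate the effects of several behaviours.

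The cost is wording changes, a minor analysis specification and a narrower stated conclusion. Data collection and sample size do not change.
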